### 5.1 Enrolled Population

The Enrolled Population will include all subjects who completed the enrollment procedures as specified in the Enrollment Procedures section (Section 3.4.5) of the protocol.

### 5.2 All Treated Population

The All Treated Population will include all enrolled subjects who received  $\geq 1$  dose of study drug.

### 5.3 Efficacy Evaluable Population

The Efficacy Evaluable Population will include all subjects in the All Treated Population who had  $\geq 1$  response assessment after the first dose of study drug.

### 6.0 STATISTICAL METHODS

### 6.1 Data Presentation

Tables and figures will be summarized by disease subgroup and cohort unless otherwise specified.

No formal tests of hypotheses will be performed. P-values, if presented, will be provided for descriptive purpose. Descriptive statistics (number of subjects, mean, and standard deviation, median, minimum, and maximum) will be presented for continuous variables including baseline demographic, disease characteristics, study drug administration, efficacy and safety outcomes. Categorical variables will be summarized as the number and percentage of subjects per category. Confidence intervals [CIs] may be included as appropriate.

### 6.2 General Conventions

Baseline is defined as the last measurement taken prior to the first dose of study drug administration. Post baseline is defined as a measurement taken after the first dose of study drug administration.

Study Day 1 is defined as the date of first dose. For visits (or events) that occur on or after first dose date, study day is calculated as (date of visit [event] – date of first dose + 1). For visits (or events) that occur prior to first dose date, study day is calculated as (date of visit [event] – date of first dose). There is no Study Day 0.

Lab data summary will be based on central labs. Local labs will be used if central labs are not available. Central labs will use reference ranges provided by the central lab and local labs will use the reference ranges provided by local labs.

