### 12.1 Adverse Events

Adverse events (AEs) will be coded using the Medical Dictionary for Regulatory Activities (MedDRA v 24.0) reporting system. Treatment-emergent AEs are defined as those events that occur on or after the first dose of study drug, through the treatment phase, and within 30 days following the last dose of study drug.

The occurrence of treatment-emergent adverse events (TEAEs) and serious TEAEs will be presented respectively by SOC and PT. If a subject experiences the same event more than once, the event will be counted only once with the greatest severity. Additionally, TEAEs and serious TEAEs will be presented by relationship and by worst severity.

Fatal (Grade 5) AEs, AEs leading to study drug discontinuation, AEs leading to study drug interruption, and AEs leading to study drug modification will be summarized.

Events of clinical interest (ECI) will be summarized. Definition of each ECI is listed in Integrated Summary of Safety (ISS), Appendix B.

For ibrutinib intolerant cohorts (8a and 8b), ibrutinib related AE will be tabulated.

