### 12.2 Hematology, Chemistry, and Immunology Parameters

Selected laboratory parameters such as AST, ALT, bilirubin, amylase, and lipase will be graded based on CTCAE 4.03. Hematologic toxicities in CLL patients will be graded by Hallek (2008) as specified in Appendix C and CTCAE 4.03. Shift tables will be presented to summarize grade shift from baseline to maximum post baseline grade. Graphs will be presented for mean or median of selected lab parameters over time as appropriate.

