### 12.4 Vital Signs and Physical Examinations

For each vital sign measurement, descriptive statistics will be presented at baseline, last post baseline, minimum post baseline, and maximum post baseline. Change from baseline at each of the last, minimum, and maximum post baseline time points will be summarized.

Findings of abnormal physical examinations will be tabulated by body system at each visit.

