### 12.7 Eastern Cooperative Oncology Group (ECOG) Performance Status

Shift of ECOG from baseline to the worst score during the treatment will be summarized in a shift table.

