### **15.0 APPENDICES**

# **Appendix A: Analysis Windows**

Tumor assessment/CT/SPD					
			Analysis Window (Study Day)		
Nominal Visit	Study Day	Nominal Month	Lower (inclusive)	Upper (inclusive)	
C2D28	56	2	2	84	
C4D28	112	4	85	140	
C6D28	168	6	141	210	
C9D28	252	8	211	294	
C12D28	336	11	295	378	
C15D28	420	14	379	462	
C18D28	504	17	463	546	
C21D28	588	19	547	630	
C24D28	672	22	631	756	
C30D28	840	28	757	924	
C36D28	1008	33	925	1092	
C42D28	1176	39	1093	1260	
C48D28	1344	44	1261	1428	
C54D28	1512	50	1429	1596	
C60D28	1680	55	1597		

Hematology / Chemistry					
			Analysis Window (Study Day)		
Nominal Visit	Study Day	Nominal Month	Lower (inclusive)	Upper (inclusive)	
C1D1	1	0		1	
C1D28	28	1	2	42	
C2D28	56	2	43	70	
C3D28	84	3	71	98	
C4D28	112	4	99	126	
C5D28	140	5	127	154	
C6D28	168	6	155	210	

CONFIDENTIAL

C9D28	252	8	211	294
C12D28	336	11	295	378
C15D28	420	14	379	462
C18D28	504	17	463	546
C21D28	588	19	547	630
C24D28	672	22	631	714
C27D28	756	25	715	798
C30D28	840	28	799	882
C33D28	924	30	883	966
C36D28	1008	33	967	1050
C39D28	1092	36	1051	1134
C42D28	1176	39	1135	1218
C45D28	1260	41	1219	1302
C48D28	1344	44	1303	1386
C51D28	1428	47	1387	1470
C54D28	1512	50	1471	1554
C57D28	1596	52	1555	

Amylase / Lipase					
			Analysis Window (Study Day)		
Nominal Visit	Study Day	Nominal Month	Lower (inclusive) Upper (inclusive)		
C1D1	1	0		1	
C1D28	28	1	2	42	
C2D28	56	2	43	70	
C3D28	84	3	71	98	
C4D28	112	4	99	126	
C5D28	140	5	127	154	
C6D28	168	6	155	210	
			Last dose	Last dose	
SFU			date +15	date +45	

Serum Ig, T cell (CD4, CD8), NK and monocyte						
	counts					
			Analysis Window			
			(Study	y Day)		
Nominal Visit	Study Day	Nominal Month	Lower (inclusive)	Upper (inclusive)		
C1D1	1	0		1		
C2D28	56	2	2	154		
C9D28	252	8	155	336		
C15D28	420	14	337	504		
C21D28	588	19	505	672		
C27D28	756	25	673	840		
C33D28	924	30	841	1008		
C39D28	1092	36	1009	1176		
C45D28	1260	41	1177	1344		
C51D28	1428	47	1345	1512		
C57D28	1596	52	1513			

B Symptoms				
			Analysis Window (Study Day)	
Nominal Visit	Study Day	Nominal Month	Lower (inclusive)	Upper (inclusive)
C1D1	1	0		1
C2D15	43	1	2	64
C3D28	84	3	65	98
C4D28	112	4	99	126
C5D28	140	5	127	154
C6D28	168	6	155	210
C9D28	252	8	211	294
C12D28	336	11	295	378
C15D28	420	14	379	462
C18D28	504	17	463	546
C21D28	588	19	547	630
C24D28	672	22	631	714
C27D28	756	25	715	798
C30D28	840	28	799	882
C33D28	924	30	883	966

CONFIDENTIAL

C36D28	1008	33	967	1050
C39D28	1092	36	1051	1134
C42D28	1176	39	1135	1218

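### Post-baseline laboratory and vital-sign values have no end date, while treatment-emergent AEs stop 30 days after the last dose, so a later value can set the worst grade or the last value

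*SAP*

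**What the plan says.** **Post baseline.** SAP Section 6.2 states that it "is defined as a measurement taken after the first dose of study drug administration". No later section adds an end.

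**Summaries built on it.**
- Section 12.2, laboratory grades: "Shift tables will be presented to summarize grade shift from baseline to maximum post baseline grade".
- Section 12.2, serum immunoglobulins: last, minimum and maximum post-baseline values and their changes from baseline.
- Section 12.4, vital signs: "For each vital sign measurement, descriptive statistics will be presented at baseline, last post baseline, minimum post baseline, and maximum post baseline", with changes from baseline on the same basis.
- Section 12.2, plots: "Graphs will be presented for mean or median of selected lab parameters over time as appropriate". There is no restriction to time on treatment.

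**Items that do have an end.**
- Section 12.1, treatment-emergent AEs: "through the treatment phase, and within 30 days following the last dose of study drug".
- Section 12.5, concomitant medications: 30 days after the last dose.
- Appendix F, narratives: last dose +30 days, with stated exceptions for later related serious events and for AEs judged clinically significant.
- Section 12.7: "Shift of ECOG from baseline to the worst score during the treatment".

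**Visit assignment.** Section 6.3 places each assessment by its date in the Appendix A windows. The hematology/chemistry table and the immunology table (serum Ig, T cells, NK cells, monocytes) have no follow-up row, and their last windows have no upper limit. Only the table headed "Amylase / Lipase" has a safety follow-up (SFU) row, which runs from last dose +15 to last dose +45 days.

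**The concern.** A maximum, minimum or last value is easily determined by a single late measurement, so these summaries depend heavily on where the observation period ends. The SAP sets an end for AEs, concomitant medications, narratives and ECOG, but none for laboratory and vital-sign values. The same calendar date can then count as post baseline for a laboratory grade and fall outside the reporting period for an AE.

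If such values exist, the shift tables could show as the worst grade a value measured well after treatment stopped. The last post-baseline value might not describe the patient on treatment, and by-visit laboratory curves could mix subjects on and off drug under a scheduled visit label. The study has no comparator arm against which to judge such values. Section 1.0 says that its safety data have supported regulatory submissions.

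**Working it through.** No sample size, power or alpha figure is involved, and the SAP gives no figure to reproduce. The check compares the definitions and then applies the Appendix A windows to a subject.

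**Step 1. End of each safety interval.**

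| Item | SAP section | End |
|---|---|---|
| Treatment-emergent AEs | 12.1 | last dose +30 days |
| Concomitant medications | 12.5 | last dose +30 days |
| Narratives | Appendix F | last dose +30 days, with exceptions |
| ECOG worst score | 12.7 | during treatment |
| Laboratory maximum grade | 12.2 with 6.2 | none stated |
| Immunoglobulin last, min, max | 12.2 with 6.2 | none stated |
| Vital-sign last, min, max | 12.4 with 6.2 | none stated |

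**Step 2. Worked subject.** The last dose on Day 56 is an assumption for illustration.
- End of the treatment-emergent window: 56 + 30 = Day 86.
- Chemistry value on Day 180: 180 − 56 = 124 days after the last dose.
- It is after the first dose, so Section 6.2 makes it post baseline.
- Hematology/chemistry window for C6D28: Days 155 to 210. Day 180 falls inside, so the value is tabulated as C6D28 and can set the maximum grade.
- An AE starting on Day 180 is after Day 86, so it is not treatment-emergent.

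**Step 3. Open last windows.** The hematology/chemistry window for C57D28 starts on Day 1555 and the immunology window for C57D28 starts on Day 1513. Neither has an upper limit. Vital signs have no Appendix A table, so the visit-window problem does not extend to them.

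**Step 4. Amylase/lipase overlap.**
- The scheduled post-baseline windows run without a gap from Day 2 to Day 210.
- The SFU window starts at last dose +15. It overlaps a scheduled window whenever last dose + 15 ≤ 210, that is, last dose ≤ 210 − 15 = Day 195.
- For the subject in Step 2, SFU runs from 56 + 15 = Day 71 to 56 + 45 = Day 101. It overlaps C3D28 (Days 71 to 98) and C4D28 (Days 99 to 126). A draw on Day 90 fits both C3D28 and SFU, and no rule chooses between them.

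**Step 5. SFU window against the AE window.** Length of SFU: 45 − 15 + 1 = 31 days. Days beyond +30: 45 − 31 + 1 = 15 days, and 15/31 = 48%. This is a share of calendar days in a window centred on +30, not a share of samples or subjects.

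**The case against.** The strongest defence is that the gap may have little practical effect. The duration of laboratory and vital-sign collection after the last dose is a matter for the protocol. The only post-treatment laboratory window in the SAP is centred on day +30, and Sections 7.0 and 11.2 refer to a Safety Follow-up visit. That fits routine collection ending near +30, in which case the excess would be about 15 days at most. All affected outputs are descriptive, since Section 6.1 rules out formal tests.

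Much of this stands, and it limits what can be claimed. Four stronger readings are tempting but not supported.
- A reader might infer that values are in fact collected long after treatment or under the next anticancer therapy. The evidence offered would be Section 11.2, which makes a blood count part of an adequate assessment. That section is an efficacy censoring rule. It censors at the last assessment before new therapy and does not say which values enter the safety laboratory data.
- A reader might infer that the excess is unbounded, or largest in cohorts with early discontinuation. The rule has no bound, but the SAP gives no figure for the data.
- A reader might take any follow-up value labelled as a scheduled visit as proof of a mismatch with the AE window. A last dose on Day 60 with a blood count on Day 90 is labelled C3D28 (Days 71 to 98), but it lies exactly at last dose +30, inside the AE window.
- A reader might blame the open interval for any disagreement between shift tables and cytopenia AE tables. These need not agree in any case: Section 12.2 grades measured values, while Appendix E counts reported terms.

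The defence does not supply an end to the interval. The SAP's own rule admits later values if they exist, and the amylase/lipase overlap arises from the SAP's windows alone.

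**Conclusion.** The point holds as a defect in a stated analysis definition. As written, any laboratory or vital-sign value collected after last dose +30 days can set a worst grade, an extreme or a last value, although an AE on the same date would not count as treatment-emergent. Separately, for any last dose on or before Day 195, an amylase or lipase draw can belong to two visits with no rule to decide.

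The wording and the window overlap follow directly from the SAP. The number of affected values is unknown, because it depends on protocol collection that is not shown. The Day 56 and Day 180 case illustrates what the rule permits and is not evidence that such values exist. The point should be corrected before the safety tables are produced. It does not touch any efficacy conclusion.

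**What to change.** 1. In Section 6.2, limit post-baseline safety values used for maximum, minimum, last and by-visit summaries to those after the first dose through last dose +30 days, matching Section 12.1. Refer to this definition in Sections 12.2 and 12.4.
2. Apply the limit before Appendix A visits are assigned. Put later values in a follow-up row or a listing. For amylase/lipase, values from +31 to +45 days would stay in the SFU row but not enter the maximum grade.
3. State that the SFU window takes precedence over study-day windows where they overlap.
4. Treat any cut at the start of new anticancer therapy as a separate choice. Apply it to laboratory values and treatment-emergent AEs alike, or leave it out. Applied to laboratory values only, it would again put the two on different intervals.

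The cost is a short change to SAP wording and one programming flag. The downside is that a few late laboratory values, some possibly drug-related, would leave the shift tables. They would remain visible in the listing.

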### 6.3 Analysis Windows

For parameters summarized by visit, an analysis window will be assigned to each nominal visit. Each assessment will be assigned to an analysis visit based on the analysis window the assessment date will fall in. Details are defined in Appendix A.

### 6.4 Missing Data Handling

No imputation for missing values of efficacy endpoints. Imputation for missing dates such as AE start or end dates, prior and concomitant medication start or end dates will be documented in the programming specifications.

### 7.0 SUBJECT DISPOSITION

The number and percentage of subjects in Enrolled Population, All Treated Population, Efficacy Evaluable Population, discontinuing treatment and reasons, and not completing the Safety follow up and reasons, and time on study will be presented.

### 8.0 IMPORTANT PROTOCOL DEVIATIONS

Important Protocol Deviations (IPDs) categories are defined and managed by the study team during the IPD reviews throughout the study before database lock. These definitions of IPD categories, sub-category codes and descriptions will be used during the course of the study. The final IPD list is used to produce the summary table and by-subject listing for IPDs.

### 9.0 DEMOGRAPHICS AND BASELINE DISEASE CHARACTERISTICS

The following variables collected at baseline will be presented:

- Demographics
  - Age (years)
    - Descriptive statistics
    - o <65 vs. ≥65 years

- $\circ$  <70 vs.  $\geq$ 70 years
- Sex (male, female)
- Race
  - American Indian/Alaskan Native, African American/Black, Asian, Caucasian/White, Native Hawaiian/Other Pacific Islander or Other
  - White vs. Non-white
- Ethnicity (Hispanic or Latino, Non-Hispanic or Latino)
- Enrollment by region (United States, Ex-United States)
- Baseline disease characteristics
  - Height
  - Weight
  - Histology
    - For RR, TN, ibrutinib intolerant, and ibrutinib relapse/refractory
      - CLL
      - SLL
    - For RS/PLL
      - CLL transformed to DLBLC
      - CLL transformed to PLL
      - FL transformed to DLBCL
  - Time since initial CLL diagnosis to first dose (years) (not applicable to RS/PLL)
  - Time since initial CLL diagnosis to transformation (years) (RS/PLL only)
  - Time since transformation to first dose (years) (RS/PLL only)
  - ECOG performance status
  - Chromosomal abnormalities
    - Deletion 17p: 17p13 (TP53)
    - Deletion 11q: 11q22.3 (ATM)
    - Unmutated IGHV
  - β2-microglobulin
    - $\circ$  >3 vs.  $\leq$ 3 mg/L
    - $\circ \quad >3.5 \ vs. \leq 3.5 \ mg/L$

- Bulky disease (not applicable for RS/PLL) defined as if at least one dimension of the lymph node measurement is
  - $\circ \geq 5 \text{ cm}$
  - $\circ \geq 10 \text{ cm}$
- Rai stage derived based on variables collected at screening visit using the criteria described in Appendix B. Additionally, Rai stage collected on the eCRF will be summarized. Rai stage is not applicable to RS/PLL cohort.
- B symptom weight loss, fever, night sweats
- Number of prior systemic therapy
  - Descriptive statistics
  - $\circ$  <3 vs.  $\geq$ 3
- Type of prior systemic therapy
- Time since most recent systemic therapy (months)
- Cytopenia
  - Absolute neutrophil count (ANC)  $\leq 1.5 \times 10^{9}/L$
  - $\circ$  Hemoglobin  $\leq 11g/dL$
  - $\circ$  Platelet  $\leq 100 \times 10^{9}/L$
  - Hemoglobin  $\leq 11g/dL$  or platelet  $\leq 100x10^9/L$
  - Any of the above
- ANC (10^9/L)
  - Descriptive statistics
  - $\circ$  ANC >1.5 to <2 x10^9/L
- Absolute lymphocyte count (ALC) (10^9/L)
- Hemoglobin (g/dL)
- Platelets  $(10^{9}/L)$
- Sum of product diameter (SPD) (cm^2)
- Baseline hepatomegaly per PE
- Baseline splenomegaly per PE

### **10.0 MEDICAL HISTORY**

Medical history will be summarized by system organ class (SOC) and preferred term (PT). Recurrence of ibrutinib related adverse events prior to first dose of study drug will be summarized by preferred term in a shift table for ibrutinib intolerant cohort (8a and 8b) only.

### **11.0 EFFICACY ANALYSIS**

Response will be assessed by investigators based on Hallek 2008 with incorporation of the clarification for treatment-related lymphocytosis per Cheson 2012 for CLL/SLL and Cheson 2014 for Richter's Syndrome.

### 11.1 Overall Response Rate (ORR)

ORR is the proportion of subjects who achieve complete remission (CR), CR with incomplete marrow recovery (CRi), or partial remission (PR) while on treatment before the initiation of new anti-cancer therapy or stem cell transplant. The corresponding 95% CIs using exact binomial distribution will be provided.

ORR will be summarized using Efficacy Evaluable Population and All Treated Population. Efficacy Evaluable Population is the primary analysis population.

For CLL disease subgroups (ie, except RS/PLL disease subgroup), ORR including PRL as a response will also be summarized in the same fashion.

### 11.2 Progression-free Survival (PFS)

PFS is defined as the time from the date of first dose to the date of first disease progression or death, due to any cause. If a subject does not experience any disease progression or death, the subject will be censored at the date of last adequate assessment (censoring date). If a subject receives an autologous or allogeneic stem cell transplant, the subject will be censored at the date of transplant. If a subject starts new anticancer therapy before disease progression or death, the subject will be censored at the date of last adequate assessment prior to receiving the new anticancer therapy. Adequate assessment is defined as physical examination (PE) and complete blood count (CBC) or computed tomography (CT) for CLL disease subgroups (or PET-CT for RS/PLL disease subgroup) and CBC. If a subject does not have any adequate assessment after first dose, the subject will be censored at Day 1.

PFS is calculated as date of disease progression or death (censoring date for censored subjects) - first dose date + 1.

Situation	Outcome	Date	Event Description/ Censoring Reason
Documented PD	Event	Earliest date of disease	PD

Events and censoring rules for PFS are summarized as follows:

CONFIDENTIAL

		assessment documenting PD	
Death	Event	Date of death	Death
Start of new anticancer therapy before documented PD or death	Censored	Date of last adequate assessment prior to receiving the new anticancer therapy	New anticancer therapy
Start of transplant	Censored	Date of transplant	Transplant
Withdrawal of consent before documented PD or death	Censored	Date of last adequate disease assessment	Withdrawal of consent
Loss to follow-up before documented PD or death	Censored	Date of last adequate disease assessment	Loss to follow-up
No documented PD or death and the reason for not completing Safety Follow-up visit is "Other"	Censored	Date of last adequate disease assessment	Other: specify
No documented PD or death at the time of data cutoff	Censored	Date of last adequate disease assessment	Data cutoff
No post-baseline adequate disease assessments	Censored	Date of first dose	No post-baseline adequate disease assessments

Kaplan-Meier (KM) curve will be used to estimate the distribution of PFS. Median PFS and the 95% confidence limits and PFS rates for selected landmarks with 95% confidence intervals will be reported. Number of progressions, deaths, and censored events by reason will be summarized.

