### 11.3 Duration of Response (DOR)

DOR is defined as the time from the date of achieving the first CR, CRi, or PR to the date of disease progression or death due to any cause, whichever comes first. Subjects who do not have a disease progression or death will be censored using the same rule for PFS as described in Section 11.2.

DOR is calculated as date of disease progression or death (censoring date for censored subjects) – date of achieving the first CR, CRi, or PR + 1.

Kaplan-Meier (KM) curve will be used to estimate the distribution of DOR. The same summary statistics for PFS will be presented for DOR.

For CLL disease subgroups (ie, except RS/PLL disease subgroup), DOR including PRL as one of the responses will also be summarized in the same fashion.

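### In SAP Section 11.2 the transplant censoring rule for PFS lacks the condition that no progression or death came first, and it uses a different censoring date from the new-therapy rule

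*SAP*

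**What the plan says.** Section 11.2 sets the endpoint first: "PFS is defined as the time from the date of first dose to the date of first disease progression or death, due to any cause". The first row of its events table makes documented progression an event, dated at the earliest assessment that shows it.

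The transplant rule follows in the text: "If a subject receives an autologous or allogeneic stem cell transplant, the subject will be censored at the date of transplant". The table repeats it in a row labelled "Start of transplant", with outcome censored and date of transplant.

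The rule for new therapy differs in two ways. It is conditional: "If a subject starts new anticancer therapy before disease progression or death". It also uses another date: "the subject will be censored at the date of last adequate assessment prior to receiving the new anticancer therapy". Its table row keeps the condition: "Start of new anticancer therapy before documented PD or death". Other rows are limited in the same way, for example "Withdrawal of consent before documented PD or death". The loss-to-follow-up row carries the same condition, and the rows for other reasons and for data cutoff require that no progression or death was documented.

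Section 11.3 (DOR) says that subjects without progression or death "will be censored using the same rule for PFS as described in Section 11.2".

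**The concern.** There are two separate problems.

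**Missing condition.** Every other censoring row that could follow a progression is limited to subjects with no earlier progression or death. The transplant row is not. Read literally, it replaces a documented progression with a later censored time, which raises the Kaplan-Meier curve. The definition and the event row point the other way, and no order of precedence is given. The result then depends on how the programmer orders the conditions.

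**Different date.** A progression-free subject who is transplanted stays in the risk set up to the transplant, whether or not disease was assessed near that day. A progression-free subject who starts new therapy leaves at the last adequate assessment. A subject who has both has two censoring dates. Section 11.1 places new therapy and transplant under one cut-off for ORR, so the split in Section 11.2 is unexplained.

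PFS and DOR are secondary objectives (Section 2.0), and results are reported by disease subgroup and cohort (Section 6.1). Several cohorts are planned at 30 subjects or fewer (Table 2).

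**Working it through.** The plan states no figure on this point to reproduce. The check compares the rules, takes visit gaps from Appendix A, and adds an illustration on stated assumptions.

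**1. Progression, then transplant.** Take progression on Day 112 (nominal C4D28) and transplant on Day 160 (assumed).

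| Rule in Section 11.2 | Outcome | Day |
|---|---|---|
| PFS definition and documented-progression row | Event | 112 |
| Transplant sentence and row, read literally | Censored | 160 |

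Both rows apply and neither yields to the other. For DOR the same subject, if a responder, is an event, because Section 11.3 borrows the censoring rule only for subjects without progression or death. The literal reading would make one subject an event for DOR and censored for PFS.

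**2. Transplant without progression.** Appendix A gives these nominal days:
- Tumor/CT: 56 days apart to Day 168, 84 days apart to Day 672 (C24D28), then 168 days apart (next Day 840).
- Hematology: 28 days apart to Day 168, then 84 days apart.

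Unassessed time credited = transplant day − day of last adequate assessment. The longest gap with no missed visit comes from a transplant the day before the next visit:
- 84-day spacing: 251 − 168 = 83 days; 83 / 30.4375 = 2.73 months.
- CT after Cycle 24: 839 − 672 = 167 days; 167 / 30.4375 = 5.49 months.

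Which gap applies depends on whether the adequate assessment is physical examination with CBC or imaging. The first figure assumes that physical examination follows the hematology visits. Missed visits would lengthen either gap. Under the new-therapy date the credited time is 0.

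**3. Possible effect in a cohort of 30 (illustration only).** The SAP gives no number or timing of transplants.

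*Lost progressions.* Assumptions: 30 event times at evenly spaced quantiles of an exponential distribution with median 6 months; *k* randomly chosen progressions re-coded as censored at a transplant 2 months later; 2,000 draws.

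| *k* re-coded | Mean estimated median (months) | Mean 6-month PFS |
|---|---|---|
| 0 | 5.72 | 0.50 |
| 1 | 6.00 | 0.51 |
| 2 | 6.33 | 0.53 |
| 3 | 6.65 | 0.54 |
| 5 | 7.46 | 0.57 |

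*Date difference alone.* Assumptions: exponential PFS with median 6 months; 1 to 3 progression-free transplants; last assessment between months 1 and 6; censoring 48 days later. The 6-month PFS rate rises by about 0.4 to 1.2 percentage points and the median by at most about 0.2 months. For scale, the standard error of a 50% rate in 30 uncensored subjects is √(0.5 × 0.5 / 30) = 0.091, or 9.1 points.

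**The case against.** The best defence of the text is that PFS has already ended at the first progression, so a later transplant has nothing left to censor. The event row comes first in the table, and the transplant sentence directly follows one about subjects with no progression or death. The row for no post-baseline assessment also lacks the condition, which suggests that event rows are meant to be read first. This is probably what the authors intended. It does not settle the matter: the plan never states that order, and it writes the condition into the neighbouring rows.

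On the date, a specific transplant rule may be taken to override the general new-therapy rule, and censoring at transplant is a choice that some analysts make. That would remove the double date, but only if the plan said so, and the unassessed time would remain.

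It is also fair that the stakes are low. Section 6.1 plans no formal tests, and Section 11.2 reports censoring by reason with transplant as its own category, so the affected subjects would be visible.

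A reader might infer three stronger things that the SAP does not support:
- **That DOR also loses progressions.** The opening condition in Section 11.3 excludes this.
- **That conditioning or bridging therapy always triggers both rules.** The SAP does not mention such therapy or classify it as new anticancer therapy.
- **That transplants cluster in the Richter's/PLL cohort.** The SAP gives no transplant counts.

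**Conclusion.** The point holds as an internal conflict and an inconsistent censoring date. For PFS, progression followed by transplant meets contradictory rows with no stated precedence. A progression may be lost if the transplant row is applied literally, but a reader should not conclude that it will be, because the definition and the event row say otherwise. For both PFS and DOR, progression-free transplanted subjects are credited with unassessed time, up to about 83 days at 84-day spacing or about 167 days if late CT governs, assuming that visits are kept.

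Both problems, where they act, push the estimates upward. In the illustration the date difference alone is small beside the sampling error of a 30-subject cohort; re-coding several progressions would matter more. The actual size is unknown without transplant counts and is probably small. The change is still worth making, because it is cheap and removes a rule that contradicts the endpoint definition.

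**What to change.** Amend Section 11.2, in both the sentence and the table row:
- Limit the rule to stem cell transplant that starts before documented progression or death, and censor at the date of the last adequate assessment prior to transplant.
- State that progression or death documented before transplant is an event.
- State that if both new anticancer therapy and transplant occur, the earlier one governs.

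DOR follows through the reference in Section 11.3 and needs no separate text. If the team prefers to keep the transplant date, it should give the reason and still add the condition and the precedence statement.

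The cost is one wording edit and one programming condition. The downside is that PFS and DOR estimates may become slightly shorter.
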